### 7.9.2 HPA axis suppression/ ACTH challenge test

For subjects assigned to the MC2-01 cream, adrenal function will be assessed in a challenge test with an intravenous dose of adrenocorticotropic hormone (ACTH) (cosyntropin). Measurement of serum cortisol levels pre- and post- stimulation with cosyntropin 0.25 mg is the accepted standard method used to evaluate adrenal suppression. The ACTH challenge test will be performed at Visit 1/Day 0, Week 4 and Week 8 visits. The test consists of blood sampling starting at 8 am ( $\pm$  30 minutes). Following the blood sample, an intravenous bolus injection of 0.25 mg cosyntropin is given at time zero (t=0 minutes). Serum cortisol concentration at t=30 minutes will reflect

stimulation of the adrenal glands induced by cosyntropin. The ACTH challenge test must be performed before application of the IP.

Since many people do not respond to the degree expected with cosyntropin stimulation, the following criteria have been established to denote a normal response:

1. pre-stimulation cortisol levels  $>5 \mu\text{g/dL}$  will be considered normal,
2. the 30-minute post-stimulation level should show an increment of  $\geq 7 \mu\text{g/dL}$  above the basal level, and
3. the 30-minute post-stimulation level should exceed  $18 \mu\text{g/dL}$ .

Therefore, a basal serum cortisol level  $\leq 5 \mu\text{g/dL}$ , or a 30-minute post-stimulation level  $\leq 18 \mu\text{g/dL}$ , or a post-stimulation increase (over basal)  $< 7 \mu\text{g/dL}$  constitutes the definition of HPA axis suppression in the trial.

Visit 1/Day 0: If HPA axis is suppressed at Visit 1/Day 0, the subject should be contacted because the application with the investigational product (IP) should be discontinued and an Early Termination visit should be performed (see [Section 7.16](#)).

Week 4: If HPA axis is suppressed at Week 4, the subject should be contacted and the application with the MC2-01 cream should be discontinued. The subject should continue in the trial and the ACTH challenge test is repeated at the Week 8 visit. If HPA axis suppression is noted at Week 8, the subject must return for a follow-up visit (see [Section 7.15](#)).

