#### **8.8.1 HPA-axis suppression**

The number and proportion of subjects with HPA-axis suppression at Week 4 and Week 8 will be summarised.

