## 8. ANALYSIS POPULATIONS

Three analysis populations will be defined for analysis:

- Safety Population: will include all randomized subjects who have been dispensed the trial medication, excluding subjects who return all of the trial medication unopened. The Safety Population will be used for all safety analyses other than evaluation of the HPA-axis.
- HPA population: will include all subjects in the Safety population that are assigned to MC2-01 cream and who show normal HPA function at Baseline (defined as a 30-minute post-stimulation cortisol level  $\geq 18 \mu\text{g/dL}$ ). Since the objective of the analysis is to estimate the risk to subjects with normal HPA function of HPA-axis suppression following treatment, subjects who meet the definition of HPA-axis suppression at Baseline will be excluded from the analysis. The HPA population will be used for the HPA axis suppression analysis.
- Pharmacokinetic (PK) Population: will include all subjects in the Safety population who have received the planned application of treatment at the Week 4 or Week 8 visit, respectively, and have had at least one post-application blood draw for PK assessment at the corresponding visit. The PK Population will be used for the PK analysis.

---

All safety, HPA and PK analyses will be conducted according to the treatment actually received.

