## 9. DATA CONVENTIONS FOR ANALYSIS

### 9.1 General Statistical Principles

All statistical processing will be performed using the SAS system (Version 9.3 or higher).

All observed and derived variables (e.g., change from baseline) used in the summaries of analyses will be presented in by-subject listings. Descriptive statistics will be used to provide an overview of the safety and PK results. For categorical parameters, the number and percentage of subjects in each category will be presented. The denominator for percentage will be based on the number of subjects appropriate for the purpose of analysis. For continuous parameters, descriptive statistics will include number of observations, mean, standard deviation (SD), median, and range. The PK parameters will be summarised using appropriate descriptive statistics including median, lower and upper quartiles, minimum and maximum. Geometric means and coefficient of variation (CV) will be provided as appropriate.

It is planned that the data from all centers that participate in this protocol will be combined so that an adequate number of subjects will be available for analysis.

No interim analyses are planned.

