## 10.8.2 Analyses of Safety Endpoints

### 10.8.2.1 HPA-axis Suppression

The number and proportion of subjects with HPA-axis suppression at Week 4 will be summarised for the HPA population. Subjects with HPA-axis suppression at Week 4, was as described in the

protocol, contacted to discontinue use of MC2-01 cream. Subjects with HPA-axis suppression at Week 8 will be summarised overall and separately by HPA-axis suppression status at Week 4.

An additional analysis of the number and proportion of subjects with HPA-axis suppression will be summarised based on the test laboratory normal reference range established for the analytical method used by the test laboratory in the trial for the ACTH challenge test.

- In this analysis HPA suppression is defined as a 30-minute post-stimulation cortisol level  $< 14 \mu\text{g/dl}$  (test laboratory normal reference range of 14 to 36  $\mu\text{g/dl}$  for the 30-minute post-stimulation cortisol level). This analysis will be performed among MC2-01 cream subjects whose Baseline cortisol level is  $\geq 14 \mu\text{g/dl}$

All HPA-axis function test results (baseline, Week 4, Week 8, and Follow-up) will be presented in a by-subject listing for the Safety population.

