Generated on XXXXXX by XXXX / Uses: XXXX / Reference: Data Listing XXXX

Table 14.2.4.1 Summary of HPA-Axis Suppression (Based on Cosyntropin US Packing Insert)  
HPA Population

	MC2-01 Cream (N=XX)
HPA-Axis Suppression, n / N (%)	
Visit 3/ Week 4	XX/XX (XX.X)
Visit 5/ Week 8	XX/XX (XX.X)
HPA-Axis Suppressed at Week 4	XX/XX (XX.X)
HPA-Axis Not Suppressed at Week 4	XX/XX (XX.X)

Note: HPA-axis suppression is defined as a 30-minute post-stimulation cortisol level <18 µg/dL  
Generated on XX/XX/XX:XXXX by XXXXX / Uses: XXXX / Reference: Data Listings XXXX

*[Programming note: Denominator for Visit 5/Week 8 (Week 4 HPA-Axis Suppressed) row is subjects with HPA-Axis Suppressed at Week 8; denominator for Visit 5/Week 8 (Week 4 HPA-Axis Not Suppressed) row is subjects with HPA-Axis Suppressed at Week 8]*

Table 14.2.4.2 Summary of HPA-Axis Suppression (Based on Lab Reference Range)  
MC2-01 Cream Subjects with Baseline Cortisol Level  $\geq$  14  $\mu$ g/dl

MC2-01 Cream (N=XX)	
HPA-Axis Suppression, n / N (%)	
Visit 3/ Week 4	XX/XX (XX.X)
Visit 5/ Week 8	XX/XX (XX.X)
HPA-Axis Suppressed at Week 4	XX/XX (XX.X)
HPA-Axis Not Suppressed at Week 4	XX/XX (XX.X)

Note: HPA-axis suppression is defined as a 30-minute post-stimulation cortisol level  $<14 \mu$ g/dL  
Generated on XX/XX/XX:XXXX by XXXXX / Uses: XXXX / Reference: Data Listings XXXX

*[Programming note: Denominator for Visit 5/Week 8 (Week 4 HPA-Axis Suppressed) row is subjects with HPA-Axis Suppressed at Week 8; denominator for Visit 5/Week 8 (Week 4 HPA-Axis Not Suppressed) row is subjects with HPA-Axis Suppressed at Week 8]*

MC2 Therapeutics  
Protocol Number: MC2-01-C3

Page X of Y

Table 14.2.5 Summary of Calcium Metabolism  
HPA Population

MC2-01 Cream (N=XX)		
	Observed Value	Change from Baseline
Albumin-Corrected Serum Calcium (unit)		
Baseline		
N	XX	--
Mean (SD)	XX.X (XX.X)	--
Median	XX.X	--
Q1, Q3	XX, XX	--
Minimum, Maximum	XX, XX	--
Visit 3/Week 4		
N	XX	XX
Mean (SD)	XX.X (XX.X)	XX.X (XX.X)
Median	XX.X	XX.X
Q1, Q3	XX, XX	XX, XX
Minimum, Maximum	XX, XX	XX, XX
Visit 5/Week 8		
N	XX	XX
Mean (SD)	XX.X (XX.X)	XX.X (XX.X)
Median	XX.X	XX.X
Q1, Q3	XX, XX	XX, XX
Minimum, Maximum	XX, XX	XX, XX

<Continue for: 24 Hours Urinary Calcium Excretion (unit) and Ratio of Urinary Calcium to Creatinine>

MC2 Therapeutics  
Protocol Number: MC2-01-C3

Page X of Y

Table 14.2.6: Summary of Physician's Global Assessment (PGA)  
Safety Population

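### SAP Tables 14.2.4.1 and 14.2.4.2 divide both Week 8 subgroup rows by the Week 8 cases, so neither row gives the proportion suppressed within its Week 4 group

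*SAP*

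**What the plan says.** SAP 10.8.2.1 asks for the number and proportion suppressed at Week 4 in the HPA population and then continues: "Subjects with HPA-axis suppression at Week 8 will be summarised overall and separately by HPA-axis suppression status at Week 4". It names no denominator for the split.

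The shells for Table 14.2.4.1 (cut-off <18 µg/dL) and Table 14.2.4.2 (cut-off <14 µg/dL) have one block, headed "HPA-Axis Suppression, n / N" with a percentage. It holds a Week 4 row, a Week 8 row and, under Week 8, one row for each Week 4 status. The same programming note stands under both tables:

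- first subgroup row: "Denominator for Visit 5/Week 8 (Week 4 HPA-Axis Suppressed) row is subjects with HPA-Axis Suppressed at Week 8";
- second subgroup row: "denominator for Visit 5/Week 8 (Week 4 HPA-Axis Not Suppressed) row is subjects with HPA-Axis Suppressed at Week 8".

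The footnote that will be printed gives only the cut-off, so a reader of the output would not see how the denominators were chosen.

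Three other statements bear on the choice:

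- SAP section 8 gives the aim of the HPA analysis as to "estimate the risk to subjects with normal HPA function of HPA-axis suppression following treatment".
- Protocol 8.8.1 says: "The number and proportion of subjects with HPA-axis suppression at Week 4 and Week 8 will be summarised".
- SAP 9.1 says: "The denominator for percentage will be based on the number of subjects appropriate for the purpose of analysis".

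Under Protocol 7.9.2, a subject suppressed at Week 4 is told to stop the cream, but "The subject should continue in the trial and the ACTH challenge test is repeated at the Week 8 visit".

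**The concern.** Two differently labelled groups have the same denominator, and that denominator is the outcome. Under this heading, and directly below overall rows that give the proportion suppressed, a reader will take each subgroup row as the proportion suppressed among the subjects of that Week 4 group. As programmed, it is the share of Week 8 cases that came from that group.

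The difference matters because HPA-axis suppression is a secondary endpoint in Protocol 4.2 and a primary safety endpoint in SAP 10.8.1. The overall Week 8 row mixes two things: suppression that persists in subjects already suppressed at Week 4, and new suppression in subjects who were not. The split is the table's only means of separating them, and with the programmed denominator neither proportion is printed.

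**Working it through.** **Inputs.** The denominators come from the two programming notes. The documents give no expected suppression rate and no size for the HPA population, so there is no figure of the plan's to reproduce and every count below is an assumption. A total of 25 tested matches the per-arm target for the PK population in Protocol 8.2. The range 20 to 30 has as its upper end half of the roughly 60 subjects to be enrolled (60/2 = 30).

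**Notation.** n = tested at both Week 4 and Week 8; s = suppressed at Week 4; p = of those, still suppressed at Week 8; k = newly suppressed at Week 8 among the other n − s.

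**Formulas.**

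| Row | As programmed | Within group |
|---|---|---|
| Suppressed at Week 4 | p/(p + k) | p/s |
| Not suppressed at Week 4 | k/(p + k) | k/(n − s) |

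The programmed rows sum to (p + k)/(p + k) = 100% whenever there is at least one Week 8 case and every case has a Week 4 result, whatever the risk in either group. If p + k = 0, both are 0/0.

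**Central example** (n = 25, s = 2, p = 1, k = 1).

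- Programmed: 1/2 = 50% and 1/2 = 50%.
- Within group: 1/2 = 50% and 1/23 = 4.3%.
- Check: the within-group rows add back to the overall Week 8 row, (1 + 1)/(2 + 23) = 2/25 = 8%. The programmed rows do not.

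**Other patterns, n = 25.**

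| s | p | k | Programmed rows | Within-group rows |
|---|---|---|---|---|
| 3 | 1 | 2 | 33.3% / 66.7% | 1/3 = 33.3% / 2/22 = 9.1% |
| 5 | 1 | 1 | 50.0% / 50.0% | 1/5 = 20.0% / 1/20 = 5.0% |
| 2 | 2 | 2 | 50.0% / 50.0% | 2/2 = 100.0% / 2/23 = 8.7% |
| 5 | 0 | 1 | 0.0% / 100.0% | 0/5 = 0.0% / 1/20 = 5.0% |
| 1 | 1 | 4 | 20.0% / 80.0% | 1/1 = 100.0% / 4/24 = 16.7% |

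In the first and last lines the order of the two rows is reversed: the programmed figures make Week 8 suppression look commoner in subjects not suppressed at Week 4, while the within-group figures show the opposite.

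**Range with one new case** (n = 20 to 30, s = 1 to 5, p = 0 or 1).

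- Row for subjects not suppressed at Week 4: programmed 1/1 = 100% (p = 0) or 1/2 = 50% (p = 1); within group from 1/29 = 3.4% (n = 30, s = 1) to 1/15 = 6.7% (n = 20, s = 5).
- Row for subjects suppressed at Week 4, with p = 1: programmed 1/2 = 50%; within group from 1/5 = 20% to 1/1 = 100%.

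**Chance that both rows are 0/0.** For a true Week 8 rate r, and subjects independent, this is (1 − r)^n.

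| r | n = 20 | n = 25 | n = 30 |
|---|---|---|---|
| 2% | 0.668 | 0.603 | 0.545 |
| 5% | 0.358 | 0.277 | 0.215 |
| 10% | 0.122 | 0.072 | 0.042 |

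**The case against.** The best defence is that the notes do what SAP 10.8.2.1 literally asks. Its Week 8 sentence takes the suppressed subjects as its subject and can be read as a breakdown of cases by Week 4 status. The row labels can be read the same way, and SAP 9.1 prescribes no particular denominator. That reading is possible, so the notes do not flatly contradict 10.8.2.1. It does not fit the rest: the meaning of N would change inside one block under one heading, with no printed explanation, and a share of cases is not the risk that SAP section 8 sets out to estimate.

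Three further points stand and limit the consequence:

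- **Recoverability.** The Week 4 row gives s, and the subgroup numerators give p and k. In the central example a reader could work out 1/2 and 1/23 from the table; the by-subject listing is needed only where tests are missing. If nobody is suppressed at Week 8, the overall row already shows that both counts are zero, so 0/0 is a fault of display rather than lost information.
- **Week 4 status is not the same as being told to stop.** Protocol 7.9.2 defines suppression by any of three criteria (basal level ≤5, 30-minute level ≤18, or rise <7 µg/dL), while the tables use <18 or <14 µg/dL alone. Some subjects told to stop will therefore fall in the row for those not suppressed at Week 4. Corrected denominators will separate subjects by Week 4 test result, and only approximately by continued use of the cream.
- **Role.** The rows are descriptive. No test, decision rule or analysis population depends on them.

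**Conclusion.** The concern holds. As written, both subgroup rows in both tables give the Week 4 status mix of the Week 8 cases, and no other part of the protocol or SAP overrides the notes. Under the assumed counts, a single new case among subjects not suppressed at Week 4 prints as 50% or 100% against a within-group 3.4% to 6.7%. At an assumed true Week 8 rate of 5% with 25 tested, there is about a 28% chance that both rows are undefined. These sizes are illustrative; the denominator fault itself does not depend on them.

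The effect is confined to two rows in each table. The notes do not touch the overall Week 4 and Week 8 rows, which carry the proportions required by Protocol 8.8.1. It should be corrected because the percentages belong to a main safety endpoint and would mislead as labelled. The wording looks like a slip, with Week 8 written for Week 4 in both denominators and a negation dropped from the second, but the documents do not confirm this.

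**What to change.** In the programming notes under Tables 14.2.4.1 and 14.2.4.2, define the denominators as follows:

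- Week 8 row for subjects suppressed at Week 4: subjects suppressed at Week 4, by that table's cut-off, with a non-missing Week 8 ACTH result.
- Week 8 row for subjects not suppressed at Week 4: subjects not suppressed at Week 4, by that table's cut-off, with a non-missing Week 8 ACTH result.

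SAP 10.8.1 already treats HPA status as missing when the post-stimulation cortisol is missing, so no new rule is needed. The numerators stay as they are, and the mix of Week 8 cases can still be read from the counts. The cost is one sentence in each of two shells, using data already collected, with no downside.

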#### **8.8.3 Adverse events**

Adverse events will be coded using Medical Dictionary for Regulatory Activities (MedDRA) terminology. Treatment-emergent adverse events will be summarized by the overall incidence of at least one event, incidence by body system, and incidence by body system and preferred term. Each subject will contribute only once (e.g., the first occurrence) to each of the rates, regardless of the number of occurrences (events) the subject experiences. Treatment-emergent AEs will be summarised by severity (mild, moderate, or severe), and by relationship to trial product (none, unlikely, possible, probable, or definite). An adverse event is treatment-emergent if its date of onset is Day 1 (Baseline) or later.

Discontinuations from the trial due to AEs and SAEs will be listed by subject.

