#### **10.8.2.3 Adverse Events**

AE terms will be coded using MedDRA dictionary (version 20.0). A treatment-emergent AE (TEAE) is defined as an AE with a start date on or after the first application to trial medication (Day 1). If relationship to study medication is missing, the event will be conservatively summarized as being related to study drug. If intensity is missing, a separate category of missing intensity will be included in the summary table, and no imputation of severity will be performed. Through the data cleaning process, all attempts will be made to avoid missing values for relationship and severity.

All AEs will be presented in a by-subject listing, detailing the verbatim term given by the investigator, the PT, SOC, whether or not related to Cosyntropin or study procedure, location of AE to treatment area, start date, stop date, intensity, outcome, relationship to study medication (definitely, probably, possibly, and not related), action taken with study medication, action taken to treat the AE, seriousness and criteria for seriousness. For subjects assigned to MC2-01 cream, all TEAEs will be assigned to the Week 1-4 (starting from Day 1 to 28) or post-Week 4 period (starting from Day 29 and after) based on onset dates. Serious AEs and AEs leading to study drug discontinuation will be presented in a separate listing.

An overall summary of AEs will be presented by treatment and by period (MC2-01 group only). The summary will include the total number of events, frequency counts and percentages with:

- Any AE
- Any TEAE
- Any serious TEAE
- Any treatment-related TEAE
- Any TEAE leading to study drug discontinuation

Summaries of the incidence of TEAEs will be displayed by treatment and by period (MC2-01 group only) according to the following:

- All TEAEs by PT in descending order of frequency (the combined frequency of both treatments)
- All TEAEs by SOC, PT, and maximum severity (mild, moderate, or severe)
- All TEAEs by SOC, PT, and maximum relationship (recorded as 'definitely', 'probably', and 'possibly') to the study drug

At each level of summarization, a subject will be counted once if he/she reported one or more events. The severity of TEAEs and relationship to study drug will be summarized in a similar manner. For summaries of relationship to study drug, a subject will be classified according to the closest relationship. For summaries of TEAE severity, a subject will be classified according to the highest severity.

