14.3.1.2	Summary of Treatment-emergent Adverse Events, Weeks 1-4 by System Organ Class and Preferred Term in Descending Frequency; Safety Population
14.3.1.3	Summary of Treatment-emergent Adverse Events, Weeks 1-4 by System Organ Class, Preferred Term, and Maximum Severity; Safety Population
14.3.1.4	Summary of Treatment-emergent Adverse Events, Weeks 1-4 by System Organ Class, Preferred Term, and Maximum Causality; Safety Population
14.3.2.1.1	Summary of Clinical Laboratory Results by Treatment and Visit, Biochemistry; Safety Population
14.3.2.1.2	Summary of Clinical Laboratory Results by Treatment and Visit, Hematology; Safety Population
14.3.2.2.1	Clinical Laboratory Results, Shifts from Baseline, Biochemistry; Safety Population
14.3.2.2.2	Clinical Laboratory Results, Shifts from Baseline, Hematology; Safety Population
14.3.3	Summary of Vital Signs by Treatment and Visit; Safety Population
14.3.4	Summary of Investigator Assessed Local Skin Reactions (LSR); Safety Population

14.3.5	Summary of Subject Assessed Local Skin Reactions (LSR); Safety Population
--------	---

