Q5: How much did treating your skin disrupt your daily routine?

Q6: Overall, how satisfied were you with the medical treatment?>>

---

SE = Standard error; LSM = Least square means; CI = Confidence interval

[1] The linear mixed effect model includes as a systematic effect and study site as a random effect.

Generated on XX/XX/XX:XXXX by XXXXX / Uses: XXXX / Reference: Data Listings XXXX

Table 14.3.1.1: Overall Summary of Adverse Events  
Safety Population

	Weeks 1 – 4 [1]		Post Week 4 [2]
	MC2-01 Cream (N=XX)	Active Comparator (N=XX)	MC2-01 Cream (N=XX)
Adverse Events			
Number of Events	XX	XX	XX
Number of Subjects, n (%)	XX (XX.X)	XX (XX.X)	XX (XX.X)
Treatment-Emergent Adverse Events (TEAEs)			
Number of Events	XX	XX	XX
Number of Subjects, n (%)	XX (XX.X)	XX (XX.X)	XX (XX.X)
Treatment-Related TEAEs			
Number of Events	XX	XX	XX
Number of Subjects, n (%)	XX (XX.X)	XX (XX.X)	XX (XX.X)
Serious AEs (All)			
Number of Events	XX	XX	XX
Number of Subjects, n (%)	XX (XX.X)	XX (XX.X)	XX (XX.X)
Serious TEAEs			
Number of Events	XX	XX	XX
Number of Subjects, n (%)	XX (XX.X)	XX (XX.X)	XX (XX.X)
AEs Leading to Study Drug Discontinuation			
Number of Events	XX	XX	XX
Number of Subjects, n (%)	XX (XX.X)	XX (XX.X)	XX (XX.X)

Note: Counts reflect number of subjects reporting one or more adverse events that map to MedDRA 20.0. A subject will be counted once only within each AE category. TEAEs include all AEs starting or worsening after the first dose of study drug.

Generated on XX/XX/XX:XXXX by SMYAE / Uses: XXXX / Reference: Data Listing XXXX

Table 14.3.1.2: Summary of Treatment-emergent Adverse Events  
by System Organ Class and Preferred Term in Descending Frequency  
Safety Population

System Organ Class Preferred Term	Weeks 1 – 4 [1]		Post Week 4 [2]
	MC2-01 Cream (N=XX)	Active Comparator (N=XX)	MC2-01 Cream (N=XX)
Subjects with any TEAE, n (%)	XX (XX.X)	XX (XX.X)	XX (XX.X)
<< Adverse Event System Organ Class >>	XX (XX.X)	XX (XX.X)	XX (XX.X)
<< Adverse Event Preferred Term >>	XX (XX.X)	XX (XX.X)	XX (XX.X)
<< Adverse Event Preferred Term >>	XX (XX.X)	XX (XX.X)	XX (XX.X)
<< Adverse Event Preferred Term >>	XX (XX.X)	XX (XX.X)	XX (XX.X)
<< Adverse Event System Organ Class >>	XX (XX.X)	XX (XX.X)	XX (XX.X)
<< Adverse Event Preferred Term >>	XX (XX.X)	XX (XX.X)	XX (XX.X)
<< Adverse Event Preferred Term >>	XX (XX.X)	XX (XX.X)	XX (XX.X)
<< Adverse Event Preferred Term >>	XX (XX.X)	XX (XX.X)	XX (XX.X)

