Note: Counts reflect numbers of subjects reporting one or more adverse events that map to MedDRA system organ class or preferred term. A subject may be counted once only in each row of the table.

[1] Includes TEAEs with an onset date on or before Week 4 visit.

[2] Includes TEAEs with an onset date after Week 4 visit.

Generated on XX/XX/XX:XXXX by SMYTEAEP / Uses: XXXX / Reference: Data Listings XXXX

*<Programming Note: sort by SOC in alphabetical order and PT in descending order of the combined frequency in the two active treatments>*

Table 14.3.1.3: Summary of Treatment-emergent Adverse Events  
by System Organ Class, Preferred Term, and Maximum Severity  
Safety Population

System Organ Class Preferred Term	Severity	Weeks 1 – 4 [1]		Post Week 4 [2] MC2-01 Cream (N=XX)
		MC2-01 Cream (N=XX)	Active Comparator (N=XX)	
Subjects with any TEAE, n (%)	Severe	XX (XX.X)	XX (XX.X)	XX (XX.X)
	Moderate	XX (XX.X)	XX (XX.X)	XX (XX.X)
	Mild	XX (XX.X)	XX (XX.X)	XX (XX.X)
		XX (XX.X)	XX (XX.X)	XX (XX.X)
<< Adverse Event System Organ Class >>	Severe	XX (XX.X)	XX (XX.X)	XX (XX.X)
	Moderate	XX (XX.X)	XX (XX.X)	XX (XX.X)
	Mild	XX (XX.X)	XX (XX.X)	XX (XX.X)
<< Adverse Event Preferred Term >>	Severe	XX (XX.X)	XX (XX.X)	XX (XX.X)
	Moderate	XX (XX.X)	XX (XX.X)	XX (XX.X)
	Mild	XX (XX.X)	XX (XX.X)	XX (XX.X)

Note: Counts reflect numbers of subjects reporting one or more adverse events that map to MedDRA system organ class or preferred term. A subject may be counted only once at the highest severity. AEs are categorized by onset date.

Generated on XX/XX/XX:XXXX by XXXXX / Uses: XXXX / Reference: Data Listings XXXX

Table 14.3.1.4: Summary of Treatment-emergent Adverse Events  
by System Organ Class, Preferred Term, and Maximum Causality  
Safety Population

System Organ Class Preferred Term	Causality Assessment[1]	Weeks 1 – 4 [1]		Post Week 4 [2] MC2-01 Cream (N=XX)
		MC2-01 Cream (N=XX)	Active Comparator (N=XX)	
Subjects with any TEAE, n (%)	Related	XX (XX.X)	XX (XX.X)	XX (XX.X)
	Not Related	XX (XX.X)	XX (XX.X)	XX (XX.X)
<< Adverse Event System Organ Class >>	Related	XX (XX.X)	XX (XX.X)	XX (XX.X)
	Not Related	XX (XX.X)	XX (XX.X)	XX (XX.X)
<< Adverse Event Preferred Term >>	Related	XX (XX.X)	XX (XX.X)	XX (XX.X)
	Not Related	XX (XX.X)	XX (XX.X)	XX (XX.X)

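### No planned table gives the cream's whole-course adverse event incidence, and the discontinuation row compares the arms over unequal windows because it is booked by onset date

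*SAP*

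**What the plan says.** SAP 10.8.2.3 provides that, for cream subjects, "all TEAEs will be assigned to the Week 1-4 (starting from Day 1 to 28) or post-Week 4 period", with onset date deciding the period. The shells of Tables 14.3.1.1 to 14.3.1.4 follow this with three columns: Weeks 1-4 cream, Weeks 1-4 ointment, and Post Week 4 cream. The notes to Tables 14.3.1.3 and 14.3.1.4 say that "AEs are categorized by onset date". In Table 14.3.1.1 the row "AEs Leading to Study Drug Discontinuation" sits in these columns, and no rule refers to the date on which treatment stopped.

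None of the four shells has a cream column for the whole course. The table outline in SAP section 14 is narrower still: it titles Table 14.3.1.3 "Summary of Treatment-emergent Adverse Events, Weeks 1-4 by System Organ Class, Preferred Term, and Maximum Severity; Safety Population", although the shell also carries a Post Week 4 column.

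Protocol 8.8 asks for the two periods to be presented separately. Protocol 8.8.3 also plans an overall incidence of at least one TEAE and states: "Each subject will contribute only once (e.g., the first occurrence) to each of the rates". Cream is applied for 8 weeks and ointment for 4 (Protocol 4.1). For exposure, Table 14.1.3 does give the cream a Day 1 to Week 8 column beside the Week 4 comparison.

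**The concern.** Booking by onset is sensible for incidence: both arms have the same four-week onset window. It leaves two gaps.

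1. **Whole-course incidence.** The cream is meant for up to 8 weeks (Protocol 2.2). A reader will want the proportion of cream subjects with any TEAE, or with a particular preferred term or worst grade, over that course. A subject with events in both periods appears in both cream columns, so the sum counts that subject twice and the true figure lies somewhere below it.

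2. **The discontinuation row.** A stop has its own date, which can be weeks after the AE began. A cream AE that starts on Day 20 and leads to a stop on Day 40 is printed as a Weeks 1-4 discontinuation. An ointment AE still open at Week 4 cannot lead to a stop, because treatment has ended. In this row the arms are followed under treatment for different lengths of time, and the Post Week 4 column omits stops that were made in the added four weeks.

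**Working it through.** The documents give no figure on this point, and the sample size is stated not to be statistical (Protocol 8.2), so there is nothing to reproduce. The calculations below are illustrations.

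**Inputs.** About 60 subjects randomised 1:1 (Protocol synopsis), so N = 60/2 = 30 per arm, and one subject is 1/30 = 3.3 percentage points. Dosing lasts 28 days for ointment and 56 for cream. The event counts and the lag from onset to stop are assumptions.

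**Bounds on whole-course incidence.** With *a* subjects affected in Weeks 1-4 and *b* Post Week 4, the number affected at any time lies between max(a, b) (complete overlap) and min(N, a + b) (no overlap).

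| a | b | Lower bound | Upper bound |
|---|---|---|---|
| 1 | 1 | 1/30 = 3.3% | 2/30 = 6.7% |
| 3 | 3 | 3/30 = 10.0% | 6/30 = 20.0% |
| 6 | 6 | 6/30 = 20.0% | 12/30 = 40.0% |
| 10 | 8 | 10/30 = 33% | 18/30 = 60% |

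**Discontinuation row, by example.** Suppose 2 of 30 cream subjects have an AE that starts by Week 4 and stop because of it in Weeks 5-8. The table prints 2/30 = 6.7% under Weeks 1-4 and 0% under Post Week 4. By date of stop it would be 0/30 and 2/30.

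**Discontinuation row, under equal risk.** Assume the same risk in both arms, AE onset uniform over Days 0 to 28, an exponential lag with mean *m* days from onset to stop, and stops possible only during dosing. The probability that such an AE leads to a stop is

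- ointment: 1 − (m/28)(1 − e^(−28/m))
- cream: 1 − (m/28)(e^(−28/m) − e^(−56/m))

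| Mean lag m | Ointment | Cream, booked to Weeks 1-4 | Ratio | Share of that cream count stopped after Day 28 |
|---|---|---|---|---|
| 3 days | 0.893 | 1.000 | 1.12 | 11% |
| 7 days | 0.755 | 0.996 | 1.32 | 24% |
| 14 days | 0.568 | 0.941 | 1.66 | 40% |

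Booked by date of stop, the Weeks 1-4 ratio is 1.00 in each case. If AEs arise at the same rate in Weeks 5-8, the same 11%, 24% and 40% are the shares of stops made in Weeks 5-8 that the Post Week 4 column omits.

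**The period cut.** The SAP text starts the "post-Week 4 period (starting from Day 29 and after) based on onset dates". The footnotes to Table 14.3.1.2 cut at the visit instead: "1] Includes TEAEs with an onset date on or before Week 4 visit" and "2] Includes TEAEs with an onset date after Week 4 visit". The protocol sets the Week 4 visit at Day 28 ± 2, counting Visit 1 as Day 0; SAP 9.2 counts the first application, at Visit 1, as Day 1. The visit therefore falls on SAP Day 27 to 31, nominally Day 29. An AE starting on a nominal visit day is Post Week 4 by the text and Weeks 1-4 by the footnote. Table 14.3.1.1 carries the markers [1] and [2] with no footnotes beneath it.

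**The case against.** The protocol prespecifies the two periods, and onset booking implements them openly. The SAP's by-treatment-and-by-period wording can be read to include a whole-treatment summary, and by-subject listings let anyone derive one. With about 30 subjects per arm this is manageable by hand. That is all true, but no shell provides the column, and adding it does not conflict with Protocol 8.8.

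Several stronger readings are tempting, and the documents do not support them.

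- A reader might infer that late cream stops disappear from the report. They do not. They are counted under Weeks 1-4; Listing 16.2.7.3 gives each discontinuation AE with its onset, end and period; and Listing 16.2.1.2 gives the last dose. Table 14.1.1 also counts withdrawals for unacceptable AEs over the whole trial, though these are trial rather than drug discontinuations.
- A reader might infer that the whole Weeks 1-4 comparison is biased, or that it favours the cream. TEAE incidence there is fairly compared. Only the discontinuation row has unequal treatment windows, and in Weeks 1-4 it counts against the cream.
- A reader might infer that this panel is the only randomised safety comparison. Laboratory values, vital signs and local skin reactions are also shown by arm, and Protocol 8.8 names HPA suppression and calcium changes as the primary safety endpoints.
- A reader might infer that ointment AEs cannot worsen or become serious after Week 4. Related AEs are followed until resolved or stable (Protocol 7.13.1), and unresolved related ones require a follow-up visit (Protocol 7.15). The asymmetry on severity is therefore weak.

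Rebooking stops by last-dose date would bring its own error. After Week 4, clear subjects may stop and restart (Protocol 6.4), so the last dose need not be the AE-driven stop. Replacing onset booking altogether would also leave Post Week 4 stops with no matching Post Week 4 TEAE. Both objections stand and shape the fix.

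**Conclusion.** The point holds as a gap in presentation. The planned AE tables cannot yield the cream's whole-course incidence for any TEAE, for a preferred term or for a worst severity; at assumed counts of 10/30 and 8/30 the uncertainty runs from 33% to 60%. For the discontinuation row alone, adding the two columns comes close to the total, since a subject is counted twice only with stop-related AEs in both periods. The defect there is the unequal window.

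The 1.12 to 1.66 ratios depend on an assumed lag distribution and on equal risk; they show direction and plausible scale and predict nothing about this trial. With few stops, the practical effect may be one or two subjects, at 3.3 points each. The randomised comparison of Weeks 1-4 TEAE incidence is sound. The conflict between the Day 28 cut and the Week 4 visit cut is certain and needs no assumption.

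**What to change.** 1. Add a cream column, Day 1 to end of trial, to Tables 14.3.1.1 to 14.3.1.4, counting each subject once at worst severity and closest relationship. Label it as cream only, since the ointment has no 8-week counterpart. Align the titles in the table outline with the shells.
2. Keep onset-date booking for incidence. In the Weeks 1-4 discontinuation row also show, for both arms, the number whose AE-driven stop occurred by the Week 4 visit, with later cream stops shown separately. Use the date of the AE-related stop, not simply the last-dose date, and state how it is derived, for example from the action-taken field and the diary's application dates.
3. Use one period cut throughout SAP 10.8.2.3 and the footnotes, and print those footnotes under Table 14.3.1.1. Also reconcile the row label, which says AEs, with the text, which says TEAE.
4. State how a stop prompted by a Week 4 HPA result (Protocol 7.9.2) enters the row if it is recorded as an AE; the documents do not say whether it is.

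The cost is SAP wording, one column and one derivation. The planned listings already hold AE dates, action taken and application dates, so no new data collection should be needed. It should be settled before the tables are run.
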